NCT02651688

Study ID: ZA-205

Title: A Randomized, Double Blind, Placebo-Controlled, Multi-Center Study in Men with Acquired Hypogonadotropic Hypogonadism to Compare Changes in Body Composition and Metabolic Parameters with Diet and Exercise in Conjunction with Treatment with 12.5 mg or 25 mg Enclomiphene

Protocol Amendment 4 Date: 09 December 2016

*Any inconsistent numbering or deletion of pages is due to the removal of a full protocol due to its summary of changes being supplied.

ZA-205 Amendment 1 Protocol Summary of Changes

Protocol Title: A Randomized, Double Blind, Placebo-Controlled, Multi-Center Study in Men with Acquired Hypogonadotropic Hypogonadism to Compare Changes in Body Composition and Metabolic Parameters with Diet and Exercise in Conjunction with Treatment with 12.5 mg or 25 mg Enclomiphene

Changes From: From Original Protocol dated December 14, 2015 To: Protocol Amendment 1 dated February 2, 2016

Reason for Amendment: To add 24-hour T and enclomiphene steady state PK assessments after 12 weeks of treatment

Changes to Protocol: Significant changes to the protocol are listed below.

SECTION	CHANGED FROM	CHANGED TO	REASON FOR CHANGE

PROTOCOL SYNOPSIS: Study Purpose
 
Study Design and Duration of treatment
 
Number of Subjects
 
[REDACTED]
		
Statement added:
 
[REDACTED]
 
[REDACTED]
 
[REDACTED]
 
[REDACTED]
	
[REDACTED]

ZA-205 Amendment 1 Protocol Summary of Changes

SECTION	CHANGED FROM	CHANGED TO	REASON FOR CHANGE

[REDACTED]
 
Statistical Methods
		
[REDACTED]
 
Statement added: [REDACTED]
	
Tables 1 and 2		Updated to include new assessments	
LIST OF ABBREVIATIONS		[REDACTED]	[REDACTED]
7. TRIAL OBJECTIVES		
Statement added: [REDACTED]
	[REDACTED]

8. TRIAL DESIGN
 
8.1.1 Overview of Study Design
 
8.2.2 Exclusion Criteria
	
20. Enrolled and randomized (if applicable) in a previous enclomiphene study
	
Statement added: [REDACTED]
 
20.Enrolled and randomized (if applicable) to enclomiphene in a previous enclomiphene study
	[REDACTED]
[REDACTED]		[REDACTED]	[REDACTED]

ZA-205 Amendment 1 Protocol Summary of Changes

SECTION	CHANGED FROM	CHANGED TO	REASON FOR CHANGE
		 The content of this table row is completely redacted with black boxes, obscuring all text in the 'CHANGED TO' column.	

ZA-205 Amendment 2 Protocol Summary of Changes

Protocol Title: A Randomized, Double Blind, Placebo-Controlled, Multi-Center Study in Men with Acquired Hypogonadotropic Hypogonadism to Compare Changes in Body Composition and Metabolic Parameters with Diet and Exercise in Conjunction with Treatment with 12.5 mg or 25 mg Enclomiphene

Changes From: From Original Protocol dated December 14, 2015 To: Protocol Amendment 2 dated July 1, 2016

Reason for Amendment: To add 24-hour T and enclomiphene steady state PK assessments after 12 weeks of treatment (selected sites) and new questionnaire

Changes to Protocol: Significant changes to the protocol are listed below.

SECTION	CHANGED FROM	CHANGED TO	REASON FOR CHANGE

PROTOCOL SYNOPSIS:   Number of Subjects 
		  
Statement added: Fifteen (15) of these subjects will be offered the opportunity to participate in the 24-hour testosterone and enclomiphene T subjects to be performed after 12 weeks of treatment.
 	

ZA-205 Amendment 2 Protocol Summary of Changes

SECTION	CHANGED FROM	CHANGED TO	REASON FOR CHANGE
[REDACTED]	[REDACTED]	[REDACTED]	[REDACTED]
[REDACTED]	[REDACTED]	[REDACTED]	[REDACTED]
LIST OF ABBREVIATIONS	[REDACTED]	Updated to include PK parameters	Addition of PK assessments
[REDACTED]	[REDACTED]	[REDACTED]	[REDACTED]
8. TRIAL DESIGN 8.1.1 Overview of Study Design 8.1.7 Subject Questionnaires 8.2.2 Exclusion Criteria	20. Enrolled and randomized (if applicable) in a previous enclomiphene study	[REDACTED] [REDACTED] 20.Enrolled and randomized (if applicable) to enclomiphene in a previous enclomiphene study	[REDACTED] [REDACTED] Clarification

ZA-205 Amendment 2 Protocol Summary of Changes

SECTION	CHANGED FROM	CHANGED TO	REASON FOR CHANGE
[REDACTED]		[REDACTED]	C
10. [REDACTED]		[REDACTED]	C
13. STATISTICAL METHODS [REDACTED]		[REDACTED]	C

ZA-205 Amendment 2 Protocol Summary of Changes

SECTION	CHANGED FROM	CHANGED TO	REASON FOR CHANGE
		

	

		

	

ZA-205 Amendment 3 Protocol Summary of Changes

3. PROTOCOL SYNOPSIS

[figure not shown]
Test Drugs:	Enclomiphene 12.5 and 25 mg capsules, and placebo
Protocol Number:	ZA-205
Study Purpose:	
To compare the effects of 12 months of treatment with enclomiphene 12.5 mg, 25 mg, or placebo capsules on body composition and metabolic parameters in overweight men with acquired hypogonadotropic hypogonadism (confirmed morning $T \leq 300$ ng/dL) following a 6 month diet and 15 month exercise program. Subjects must not have been treated with testosterone products in the 6 months prior to the study and must not ever have used testosterone products for a year or longer.
 
[REDACTED]

Study Design and Duration of Treatment:	
Protocol ZA-205 is a randomized, double-blind, placebo-controlled multi-center study to compare changes in metabolic parameters following treatment with 12.5 mg or 25 mg of enclomiphene or placebo in conjunction with a 6-month diet and 15 month exercise program, in overweight men with acquired hypogonadotropic hypogonadism. Subjects will receive a 15-month gym membership with personal trainer for 12 months, a Fitbit and a 6 month commercial diet program. The study requires 7 clinic visits and is approximately 15 months in duration. Subjects will be treated with enclomiphene or placebo for 12 months.
 
[REDACTED]
 
The study will enroll 45 male subjects, 15 randomized to treatment with enclomiphene 12.5 mg, 15 randomized to treatment with 25 mg enclomiphene, and 15 randomized to Placebo, in a 1:1:1 ratio.
 
Eligible subjects must have 2 consecutive assessments of morning testosterone ≤ 300 ng/dL. LH must be >1.4 mIU/mL and below 9.4 mIU/mL at Screening. Waist circumference must be ≥ 40 inches (101.6 cm). Efficacy assessments will include weight, BMI, waist circumference, lean body mass, and metabolic parameters.
 
[REDACTED]

Subject Population	
The study will enroll overweight males, aged 18-60, with secondary hypogonadism and confirmed morning testosterone levels ≤ 300 ng/dL, with a waist circumference ≥ 40 inches (101.6 cm), who must not have been treated with testosterone products in the 6 months prior to the study and must not ever have used testosterone products for a year or longer.

Statistical Methods:	
Although this study is considered hypothesis generating, a Statistical Analysis Plan (SAP) will be prepared prior to the unblinding of the study that documents all planned analyses and data assumptions. Interim analyses will be conducted after all subjects have been assessed for 6 and 12 months.
 
For all subjects included in this study, subject accountability, baseline demographic and medical history data will be summarized for each treatment group. Summaries for quantitative variables include the sample size, mean, median, standard deviation, minimum, and maximum. Summaries for categorical variables include the number and percent of patients for each outcome.
 
Analyses will focus on descriptive statistics for each efficacy endpoint with between and within treatment comparison conducted. It is hypothesized that subjects treated with enclomiphene will have additional improvements in testosterone, body composition, weight, waist circumference and assessments of metabolic parameters.
 
Safety and tolerability [REDACTED] will be summarized for each treatment group separately. Summaries for quantitative variables include the sample size, mean, median, standard deviation, minimum, and maximum. Summaries for categorical variables include the number and percent of patients for each outcome. Where applicable, statistical testing of the safety data to compare the treatment groups is anticipated.
 
[REDACTED]

[figure not shown]

5. LIST OF ABBREVIATIONS

AE adverse event
CRF case report form

DHT dihydrotestosterone
dL deciliter
DVT deep vein thrombosis
ECG electrocardiogram
FSH follicle-stimulating hormone
g grams
GCP Good Clinical Practice
HbA_{1c} hemoglobin A_{1c}
hCG human chorionic gonadotrophin
Hct hematocrit
Hgb hemoglobin
HOMA-IR Homeostasis Model of Assessment – Insulin Resistance
ICH International Conference on Harmonization
IND investigational new drug
IRB Institutional Review Board
kg kilogram(s)
LBM lean body mass
LH luteinizing hormone
m meters
mg milligram(s)
mL milliliter
ng nanograms
PRO Patient Reported Outcome
PSA prostate specific antigen
RBC red blood cell
SAE serious adverse event
SHBG sex hormone binding globulin
T testosterone
TE thromboembolic
Total T total testosterone
t_{1/2} Apparent elimination half life
T_{max} Time of the maximum measured plasma concentration
λ_z Terminal elimination rate constant
VTE venous thromboembolism
WBC white blood cell

6. BACKGROUND INFORMATION

The sponsor has completed a full Phase III development program demonstrating the safety and efficacy of enclomiphene for the treatment of secondary hypogonadism. Details of non-clinical findings are provided in the Investigator Brochure.

■ [REDACTED]

[REDACTED]

[REDACTED]

■ [REDACTED]

[REDACTED]

6.3 Ethical Conduct of the Study

This trial will be conducted in strict compliance with the protocol and all applicable FDA regulations and GCP guidelines to insure Good Clinical Practice standards. The Institutional Review Board (IRB) for this study is IntegReview, [name].

7. TRIAL OBJECTIVES AND PURPOSE

The primary objective of this study is to compare the effects of treatment with enclomiphene to placebo, upon anthropometric and metabolic parameters in hypogonadal men undergoing a 6-month diet and 15 month exercise program.

Additional study objectives are to document the differences in testosterone and LH and changes from baseline in symptoms using a selection of subject questionnaires in enclomiphene-treated men compared to placebo. [REDACTED]

[REDACTED]

[REDACTED]

[REDACTED]

8. TRIAL DESIGN

8.1 Study Design

8.1.1 Overview of Study Design

Protocol ZA-205 is a randomized, double-blind, placebo-controlled multi-center study to compare changes in weight, lean body mass (using DXA), waist circumference, glycemic parameters and scores using various subject questionnaires following treatment with 12.5 or 25 mg enclomiphene or placebo in overweight men with acquired hypogonadotropic hypogonadism and waist circumference ≥ 40 inches (101.6 cm). The study requires 7 clinic visits and is approximately 15 months in duration. Subjects will be provided with a 15 month gym membership and personal trainer, and will exercise for 30-45 minutes three times a week. They will also receive a 6 month commercial diet program. Subjects will be treated for 12 months. [REDACTED]

The study will enroll 45 male subjects, 15 randomized to treatment with enclomiphene 12.5 mg, 15 randomized to enclomiphene 25 mg and 15 randomized to placebo, in a 1:1:1 ratio.

Eligible subjects must have 2 consecutive assessments of morning T at Visit 1 (screening). The assessments must be 2-4 days apart and both must be 300 ng/dL or less. Subjects must also have LH >1.4 and < 9.4 mIU/mL at Screening. Waist circumference must be ≥ 40 inches (101.6 cm). Subjects must not have been treated with testosterone products in the 6 months prior to the study. They must not have used testosterone products for 12 months or longer at any time in the past. Subjects will follow a commercial diet plan and exercise with a personal trainer at least 3 times a week. At clinic visits, clinical laboratory assessments will be performed and subject questionnaires will be administered. Subjects will be called every 2 weeks to check on compliance with their exercise regimen and diet, and solicit adverse events. [REDACTED]

8.1.2 Study Drug Accountability

The designee assigned by the Principal Investigator at each site will maintain accurate records of receipt of all study drugs, including dates of receipt. Reasons for deviation from the expected dispensing regimen must also be recorded. A Drug Dispensing Form will be provided for this purpose. To satisfy regulatory requirements regarding drug accountability and destruction,

the Principal Investigator at each site will return all unused study medication with dispensing records to the Sponsor for final accountability and disposal.

8.1.3 Randomization and Blinding

Subjects will be randomized, in a double-blinded manner, in a 1:1:1 ratio to enclomiphene 12.5 mg, enclomiphene 25 mg, or placebo.

8.1.4 Study Medication

All study drugs will be supplied by Repros Therapeutics Inc. Enclomiphene 12.5 mg and 25 mg capsules, or placebo capsules, [REDACTED] by a clinical supplies contract vendor designated by Repros Therapeutics Inc. Each bottle will have a label indicating the identification number, the number of capsules, expiration date, a statement "Caution: New Drug – Limited by Federal Law (US) to Investigational use" and instructions to take 1 capsule daily in the morning. Subjects will take one capsule with approximately 8 ounces of water.

Subjects should be instructed not to dose on the mornings of clinic visits.

Subjects will record study medication date and time on subject Drug Diary Cards. [REDACTED]

8.1.6 Lean Body Mass Assessment

Lean body mass will be assessed by DXA. For further details reference the Study Procedures Manual.

8.1.8 Waist Circumference Measurement

Waist circumference should be measured at the level of the navel to the nearest 0.5 cm. The tape should be held level. Subject should take 3 breaths and on the last exhale (normal exhale) the measurement should be taken.

8.1.11 Diet and Exercise Programs

These programs are described in more detail in the Study Procedures Manual.

The sponsor is providing a 15 month gym membership that will commence when subjects start treatment and conclude at the 3-Month follow up visit. Subjects will be assigned a personal trainer for 12 months and will be instructed to exercise for at least 30-45 minutes 3 times each week. The workout will be 60% cardiovascular training and 40% resistance training. Strength progress will be assessed from changes in leg press and chest press weights. Subjects will receive a signed letter from the investigator stating that the subject has been cleared to participate in an exercise program that the subject can provide to their trainer prior to starting their program.

Subjects will also receive a 6-month commercial diet program that they will start when they start treatment, and follow until their 6 month visit. The diet plan provides about 1500 calories/day comprised as follows: 25% of calories from lean protein, less than 30% of calories from fat, about 50% carbohydrates, low sodium (less than 2,300 mg/day) and 25-35 g fiber /day. Subjects will select the plan of their choice from those available and modify it to individual needs, if necessary, with the help of a plan dietician. The program includes counseling from a plan counselor.

After completion of the commercial diet program subjects will be counseled at each visit to continue with healthy eating habits. Subjects will be called every 2 weeks (except on days of clinic visits), to check on compliance with their diet and exercise programs and solicit any adverse events.

8.2 Selection and Withdrawal of Subjects

Subjects will be selected during screening based on the inclusion and exclusion criteria and clinical assessments listed below. Subjects will be discontinued from the study prematurely if:

- Unacceptable adverse events considered by the investigator to be associated with use of the study drug occur
- Hematocrit >54% and confirmed upon repeat
- The subject requests to be withdrawn from the study
- A need for concomitant medication prohibited by the protocol arises

- The Principal Investigator decides that it is in the subject's best interest
- The subject is noncompliant with the protocol at Sponsor/Investigator discretion

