11.1.2 Definitions

Adverse Event – Any untoward medical occurrence in a clinical investigation subject administered a drug and does not necessarily have a causal relationship with this treatment. An AE can therefore, be any unfavorable and unintended sign (including an abnormal laboratory finding if the investigator considers this finding to be an adverse event), symptom, or disease temporally associated with the use of an investigational product, whether or not related to the investigational product.

Serious Adverse Event (SAE) – An adverse drug experience that results in any of the following outcomes: death, a life-threatening experience, requires or prolongs subject hospitalization, results in persistent or significant disability/incapacity, or is a congenital anomaly or birth defect.

Venous thromboembolic events (VTE) should also be reported to the sponsor as Serious Adverse Events regardless of whether the above-defined SAE requirements are met.

Unexpected Adverse Event: Any adverse event that is not identified in nature, severity, or frequency in the current Investigator's Brochure.

Additionally, the Principal Investigator will evaluate all AEs as follows:

Action taken: whether or not the AE caused the subject/patient to discontinue the study medication.

Intensity, to be graded as:

DEGREE	DESCRIPTION
Mild	Awareness of signs and symptoms; easily tolerated
Moderate	Discomfort sufficient to interfere, but not prevent daily activity
Severe	Unable to carry out usual activity

Relationship to study medication, to be graded as:

DEGREE	DESCRIPTION
Definitely	There is evidence of exposure to the study drug, for example, reliable history or acceptable compliance assessment; the temporal sequence of the AE onset relative to the medication is reasonable; the AE is most likely to be explained by the treatment than by another cause; the AE shows a pattern consistent with previous knowledge of the treatment.
Probably	There is evidence of exposure to the study drug; the temporal sequence of the AE onset relative to medication administration is reasonable; the AE is more likely explained by the treatment than by another cause.
Possibly	There is evidence of exposure to the study drug; the temporal sequence of the AE relative to the medication administration is reasonable; the AE could have been due to another equally likely cause.
Probably not	There is evidence of exposure to the study drug; there is another more likely cause of the AE.

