12.1 Prohibited Medications

Use of any of the following medications during the study is prohibited:

- Any testosterone products other than the randomized study treatment
- Aromatase inhibitors (e.g. Anastrozole)
- Clomid
- 5 α -reductase inhibitors
- hCG
- Androgen
- Estrogen
- Anabolic steroid
- DHEA
- Herbal hormone products
- Chronic systemic steroid use (short term use is acceptable)

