13.2.3 Efficacy Analyses

The analysis of each efficacy endpoint will be conducted in the intent-to-treat (ITT) population, defined as all subjects randomized to treatment with enclomiphene or placebo. The ITT population will be determined prior to unblinding the study data and reasons for any subjects excluded will be explained in the clinical study report. Handling of missing data will be described in the Statistical Analysis Plan (SAP) [REDACTED]

[REDACTED] t will be of interest to investigate various prognostic factors, such as age and diet compliance, to determine how these affect treatment response. Those factors will be noted in the SAP.

13.2.3.1 *Lean Body Mass*

Lean Body Mass (LBM) will be determined by DXA at baseline, 6 months and end of study. The change from baseline in lean body mass will be investigated with at least two measurements:

- Percentage change in LBM
- Change in LBM percentage (%LBM)

[figure not shown]
Subjects are expected to gain LBM and percentage LBM. Within and between treatment group t-tests or appropriate non-parametric methods will assess treatment affect. Descriptive statistics will summarize the results.

13.2.3.2 *Body Strength*

Strength will be assessed over the course of the study by assessments of the maximum Leg and Chest Press weight obtained. These values will be assessed at baseline and weekly. The baseline assessment will be determined at the subject's first gym visit. Analyses will compare the periodic assessments to the subject's baseline. Within and between treatment group t-tests or appropriate non-parametric methods will assess treatment affect. Descriptive statistics will summarize the results.

13.2.3.3 *Waist Circumference*

Careful assessments of waist circumference will detect change in body composition. The change in waist circumference over the duration of the study will be calculated and summarized using descriptive statistics. The change from baseline will be compared within and between treatment groups using a t-test or appropriate non-parametric method.

13.2.3.5 *Testosterone*

For each treatment group, the T and change from baseline in T (visit value minus baseline value) will be summarized at each treatment visit using descriptive statistics (sample size, mean, median, standard deviation, minimum and maximum). The change from baseline in T will be compared within and between treatment groups using a t-test or appropriate non-parametric method.

13.2.3.6 *LH*

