6.5 SUBJECT DISPOSITION

Subject disposition will be summarized in terms of the number of subjects who completed the study and discontinued early from the study. Disposition will be summarized for each treatment group using the Intent-to-Treat population.

6.6 **DEVIATIONS**

The total number of each deviation type will be summarized for the Intent-to-Treat population.

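### Protocol 8.2 takes men out of the study, not just off study drug, and no readable text continues outcome assessment, although efficacy is analysed in all randomized men

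*Protocol*

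**What the plan says.** Protocol 8.2 introduces six triggers with "Subjects will be discontinued from the study prematurely if". Two of them read "Unacceptable adverse events considered by the investigator to be associated with use of the study drug occur" and "Hematocrit >54% and confirmed upon repeat". A third is the need for a prohibited medication; the others are the subject's request, the investigator's judgement of best interest, and noncompliance. Protocol 12.1 opens its list, which includes testosterone products, with "Use of any of the following medications during the study is prohibited".

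Protocol 11.1.2 uses different language. For each adverse event the investigator records "whether or not the AE caused the subject/patient to discontinue the study medication".

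The efficacy population in Protocol 13.2.3 is "defined as all subjects randomized to treatment with enclomiphene or placebo", with reasons for any exclusion to be explained in the study report. SAP Amendment I, sections 4.1 and 6.8, uses the same all-randomized population. SAP 6.5 summarizes disposition by the "number of subjects who completed the study and discontinued early from the study".

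On timing, Protocol 13.2.3.1 states "Lean Body Mass (LBM) will be determined by DXA at baseline, 6 months and end of study" and expects lean mass to rise. On missing values, Protocol 13.3 carries the last observation forward in some analyses, which it does not name, and imputes no change where nothing was measured after baseline. Protocol 13.2.3 defers missing-data handling to the SAP. The readable SAP text has no rule for missing efficacy data, though parts of it are redacted.

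**The concern.** An analysis of all randomized men needs outcomes from all randomized men. As worded, 8.2 ends participation at the point where a man stops drug for a reason that may be tied to his response, and neither 8.2 nor SAP 6.5 has a category for a man who is off drug but still followed.

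The reasons may not be balanced across arms. Attribution of an adverse event to study drug may be commoner on active treatment. A hematocrit above the threshold is plausibly commoner where testosterone rises. A need for a testosterone product is plausibly commoner where it does not. These mechanisms can pull in different directions, and the documents give no rates.

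At stake are the active-placebo estimates and the p-values that both documents judge at 0.05. With 15 men per arm, one man is 1/15 = 6.7% of an arm, so a few selective losses matter. Values that were never collected cannot be recovered at analysis.

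**Working it through.** The plan states no power, effect size, SD or dropout rate, so there is no figure of its own to reproduce beyond 45/3 = 15 men per arm. Both calculations below compare one dose with placebo, 15 v 15, with the outcome in SD units.

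**Step 1: set the texts side by side.**

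| Place | Event named |
|---|---|
| Protocol 8.2 | leaving the study, for every trigger |
| Protocol 11.1.2 | stopping study medication because of an adverse event |
| SAP 6.5 | completing the study or leaving it early |
| Protocol 13.2.3; SAP 4.1 and 6.8 | analysis of all randomized men |

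Stopping drug is recognised in the adverse-event section but has no counterpart in the withdrawal rule or the disposition table.

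**Step 2: analysis of observed men only.** Assumptions: the 2 men with the highest androgen response leave an active arm, the 2 with the lowest leave placebo, and this driver correlates 0.3 to 0.6 with the outcome. Simulation with 15 men and a unit-SD outcome shows that losing the 2 most extreme moves that arm's mean by 0.069 SD (correlation 0.3) or 0.137 SD (correlation 0.6). The opposite loss in the other arm doubles the shift:

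- 2 × 0.069 = 0.138 SD
- 2 × 0.137 = 0.274 SD

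In this scenario the difference moves toward zero by 0.14 to 0.27 SD. With 13 men left per arm, the standard error grows by sqrt(15/13) = 1.074, or 7%.

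**Step 3: no-change imputation from Protocol 13.3.** Let c be the mean change on placebo, delta the true difference, and kA and kP the numbers of active and placebo men removed before any post-baseline value. Then

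expected difference = (15 − kA)/15 × (c + delta) − (15 − kP)/15 × c.

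The values of c, delta, kA and kP are assumptions. With delta = 1.0, kA = 3 and kP = 0:

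- c = 0.5: 12/15 × 1.5 − 0.5 = 0.70 SD
- c = 1.0: 12/15 × 2.0 − 1.0 = 0.60 SD

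Power for a two-sided t-test at 0.05 is 75% with complete data. In 40,000 simulated trials it falls to 41% (c = 0.5) and 25% (c = 1.0).

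| Removed, active v placebo | Reads, c = 0.5 | Reads, c = 1.0 | Power, c = 0.5 | Power, c = 1.0 |
|---|---|---|---|---|
| 2 v 0 | 0.80 | 0.73 | 53% | 41% |
| 3 v 0 | 0.70 | 0.60 | 41% | 25% |
| 4 v 0 | 0.60 | 0.47 | 30% | 12% |

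**Step 4: direction.** With 0 v 3 removals, the same true 1.0 SD reads 1.5 − 12/15 × 0.5 = 1.10 SD or 2.0 − 12/15 × 1.0 = 1.20 SD, an overstatement. With no true effect, 3 v 0 removals give 12/15 × 0.5 − 0.5 = −0.10 SD or 12/15 × 1.0 − 1.0 = −0.20 SD, with type I error of 5.7% or 7.6%. Equal removal, 3 v 3, gives no bias when there is no effect, but reads a true 1.0 SD as 12/15 × 1.0 = 0.80 SD. The sign therefore depends on which arm loses more men, and who they are.

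**The case against.** The strongest reply is that the inference rests on incomplete text. Protocol section 9 (Study Procedures) and the section 4 schedule are not in the public copy, and parts of 13.2.3 and 13.3 are redacted. An early-termination visit may exist, possibly with DXA, and the end-of-study scan could mean each man's own last visit. This stands in part. A reader might infer that a man leaving at month 5 certainly has no post-baseline lean mass; the documents do not establish that. An exit visit would, however, supply one value, not those scheduled later.

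The plan also has a missing-data rule. For endpoints measured often, such as testosterone at treatment visits and strength each week, carrying the last value forward keeps a man's own observed response, so the loss is less severe than for DXA. But the analyses that use it are not named, and no change is not a neutral value when lean mass is expected to rise.

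Three further readings are tempting and not supported:

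- **Bias always toward zero.** Opposite losses in the two arms are one scenario; step 4 shows that the sign can reverse.
- **Harm from testosterone started after month 12.** A man still on study at month 12 has already reached his 12-month assessments. Losing him before month 15 does not touch the 12-month comparison.
- **Safety observation stops at withdrawal.** Protocol 11.1.3 documents serious adverse events for 30 days after the last dose, SAP 6.4 calculates each man's exposure, and SAP 6.9.1 tabulates adverse events leading to withdrawal. What may be lost is the remaining scheduled safety assessments.

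Finally, the study is hypothesis-generating and has no sample-size calculation. That lowers the stakes but does not remove them, because the plan still tests every endpoint at 0.05.

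**Conclusion.** The point holds as a gap between the withdrawal rule and the analysis population. Protocol 8.2 ends study participation for reasons that may depend on arm, no readable text continues outcome assessment, and efficacy is claimed for all randomized men. The stated fill-in rules do not remove the resulting bias, least of all for lean mass, with only two scheduled scans after baseline.

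The size is illustrative: 0.14 to 0.27 SD among observed men if 2 of 15 leave each arm in opposite directions, or a true 1.0 SD read as 0.60 to 0.70 SD if 3 v 0 early removals are imputed as no change. Both rest on assumed numbers of leavers. The first also rests on assumed correlations, and the second on an assumed placebo change of 0.5 to 1.0 SD. Neither predicts what will happen in this trial, and the direction is unknown. An early-termination procedure in the unseen sections would reduce the problem but would not replace the later scheduled values. The consequence is for interpretation of estimates and p-values. Nothing here bears on whether the clinical criteria are right.

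**What to change.** 1. **Protocol 8.2 and 11.1.2.** Reconcile the two sections on leaving the study versus stopping study medication. The clinical criteria and their clinical handling remain the sponsor's decision.
2. **Protocol 8.2.** State that men who stop study drug and still consent are asked to complete the outcome and safety assessments already scheduled: clinic measures, laboratory tests, the 6-month and end-of-study DXA, and the adverse-event calls. Record any use of a prohibited drug with its date.
3. **SAP 6.5.** Tabulate drug discontinuation and study discontinuation separately, with reasons, by arm.
4. **SAP 6.8.** Include values collected after drug discontinuation in the ITT comparison.

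The cost is a protocol amendment, matching SAP and CRF wording, and visits and scans already planned for the few men concerned. Some will decline, so missing data will be reduced rather than eliminated. Off-drug values will dilute the on-drug effect somewhat, which is the price of a comparison that reflects all randomized men.
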